15.5 Recording and Processing of Data

If using hard copies of CRF's, study center personnel will complete individual CRF's in black ink. All corrections to entered data will be made by drawing a single line through the information to be corrected without obscuring it. All corrections will be initialed, dated and explained, if necessary. **Do not use "white-out" or obscuring correction tape.** A CRF is required for every patient who received any amount of study treatment. The investigator will ensure that the CRF's are accurate, complete, legible and timely. Separate source records are required to support all CRF entries.

Patients will be entered into the Radiation Oncology Prostate Cancer Database for data collection and interpretation. The database links the patient Medical Record number to a participant's Research ID number and collects data on each patient related to biopsies and treatments.

15.6 Non-Protocol Research

No investigative procedures other than those described in this protocol will be undertaken on the enrolled subjects without the agreement of the IRB.

15.7 Ethics

The investigator agrees to conduct the study in compliance with the protocol, current good clinical practices, and all applicable (local, FDA) regulatory guidelines and standard of ethics.

15.8 Essential Documents for the Conduct of a Clinical Trial

Essential documents are those documents with individually and collectively permit evaluation of the conduct of a trial and the quality of the data produced.

The following documents (at minimum) will be on file:

- CV's and license of all investigators
- IRB documentation/correspondance
- Documentation of IRB certification
- Study Protocol
- Informed Consent Forms
- Delegation of Authority Log
- Screening and Randomization Log
- Training Documents
- Laboratory Documents

APPENDIX I. STUDY CALENDAR – MAPS

Assessment	Prior to Enrollment	After Enrollment and Prior to RT	Weekly during RT	Follow-up				
				During Last Week of RT	6 Weeks after RT	3 Months after RT	Every 6 months thereafter up to 5.25 years post-RT	Other
History & Physical Exam; Performance Status (Zubrod) Within 8 weeks prior to protocol entry and Zubrod < 2.	X		X	X	X	X	X	
Toxicity During RT and at all follow-up visits; use CTCAE 4.0.								
PSA PSA of at least 0.1 and up to 4.0 ng/mL and obtained ≤ 3 months prior to enrollment	X ^a			X	X	X	X	
Serum total testosterone Obtained ≤ 3 months prior to enrollment	X ^a							At 9 months
Blood collection for research	X ^a			X		X		At 9 months, 2-2.5 years
Bone Scan	X ^b							©If deemed necessary by treating physician
DCE-MRI and or PET of prostate bed/pelvis Obtained ≤ 3 months prior to enrollment and the enhancing lesion in the prostate bed should be at least 0.4 cc and a maximum of 6 cc	X					X		©At 9 months and 2-2.5 years
Pathology Review of outside biopsy material prior to enrollment	X							
MRI/US prostate bed biopsy If the MRI shows a new lesion, an optional MRI/US-guided biopsy may be obtained						X ^e		©At 9 months and 2 – 2.5 years post completion in case of identified by MRI lesion

EPIC- SF-12, MAX-PC After enrollment and prior to US biopsy.	X			X	X	X		At 9 months, 15 months and yearly to 5.25 years
IPSS	X			X	X	X	X	
CT simulation		X						
Note: Measurements and follow-up visits should occur within \pm 2 weeks up to the 3 month visit and within \pm 8 weeks for subsequent measurements/visits.								
See Eligibility Criteria for detailed description for evaluations.								
^a If possible, blood collected prior to enrollment should be obtained prior to androgen deprivation therapy.								
^b If deemed necessary, obtained \leq 4 months prior to enrollment								
^c To be conducted for a PSA of ≥ 2 or physician concern for metastasis.								
^d MRI at 9 months and 2-2.5 years will be obtained per the PI's discretion.								
^e Biopsy collection is optional								

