Ten of the fifteen (67%) studied patients had positive margins, two (13%) had seminal vesicle (SV) involvement, and seven (47%) had extracapsular extension. The median time to RT after prostatectomy was 18 months (3–120). Principal component analysis was applied to the DCE-MRI dataset from each patient. Visual inspection of the principal components can be extremely informative about the number and types of variations present in the data. In Figure 2, for example, the first four principal components from a DCE-MRI dataset are shown. It is clear that while the first three have a smooth character, the fourth has a spike at the 9th time-point of acquisition (marked with an arrow). Based on the corresponding score-image, it can be inferred that there was a sudden deformation of the rectum.

[figure not shown]

Figure 3. Analysis of DCE-MRI dataset from patient post-prostatectomy. Axial, coronal and sagittal views overlaid with a color map depicting the area of the tumor. Insert: Temporal contrast uptake and washout pattern of the tumor.

Indeed, a close inspection of the image data from this slice at this time point indicates changes in the rectum shape. These “flawed” series were removed from further analysis. Further, the Region of Interest (ROI) was outlined and cNMF applied, seeking as many patterns as the number of significant principal components. In Figure 3 cNMF results from another patient are presented. The area of the tumor, corresponding to the characteristic tumor temporal pattern is depicted with a heat map on the T2w sequences. It is clear that in this case a significant volume around the base of the bladder is suspicious for malignancy. Overall (73.3%) patients had findings suggestive of tumor as visualized by DCE-MRI; four of these (36%) had a palpable abnormality on digital rectal examination prior to RT. A total of 17 areas suspicious for malignancy were identified: 10 in the prostate bed; 4 in lymph nodes; and 3 in the SV remnants. Thus, our data indicate that T2w MRI, combined with DCE, detects abnormalities suggestive of residual tumor in the prostate bed in over 70% of patients evaluated for RT. Because patients treated with salvage RT often develop a rising PSA later and there is some evidence for an RT dose response, targeting of the contrast-enhancing areas specifically may improve tumor control and limit toxicity.

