3.1 Inclusion Criteria

Unless otherwise specified, the following are required at enrollment:

- A. Prostate cancer patients with a PSA after prostatectomy of at least 0.1 ng/mL and up to 4.0 ng/mL within 3 months prior to enrollment.
- B. Patients with or without palpable abnormalities on digital rectal exam (DRE) are eligible.
- C. Minimum of 3 months since prostatectomy to allow for return of urinary continence and healing.
- D. Imaging detectable lesion or lesions in prostate bed or regional LN. Each lesion should be at least 0.4 cc and a maximum of 6 cc and was obtained \leq 3 months prior to protocol entry or enrollment.
- E. No evidence of metastatic (distant) disease (pelvic nodes are allowed up to common iliac).
- F. Negative bone scan if deemed necessary by treating physician obtained \leq 4 months prior to protocol entry or enrollment..
- G. No previous pelvic radiotherapy.
- H. Serum total testosterone taken within 3 months prior to enrollment.
- I. No concurrent, active malignancy, other than nonmetastatic skin cancer or early stage chronic lymphocytic leukemia (well-differentiated small cell lymphocytic lymphoma). If a prior malignancy is in remission for \geq 3 years then the patient is eligible.
- J. Ability to understand and the willingness to sign a written informed consent document.
- K. Zubrod performance status <2.
- L. Patients must agree to fill out quality of life/psychosocial questionnaires.

M. Age ≥ 35 and ≤ 85 years.

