5.0 CLINICAL AND LABORATORY EVALUATIONS

5.1 Baseline/Pretreatment Evaluations

Prior to Enrollment

- History and physical exam, including evaluation of patient's ability to perform daily activities (Zubrod performance status) within 8 weeks prior to protocol entry.
- Blood tests within 3 months prior to protocol entry or enrollment unless otherwise indicated. Up to five tubes of blood will be collected:
 - PSA level
 - Serum testosterone .
- Blood will be collected for research fluid testsBone scan if deemed necessary by treating physician obtained \leq 4 months prior to protocol entry or enrollment.
- DCE-MRI and or PET of prostate bed/pelvis at 1.5T or 3.0T MRI (preferably 3.0T) within 3 months prior to enrollment. Identifiable DCE-MRI tumor lesion or lesions. The enhancing lesion(s) in the prostate bed should be at least 0.4 cc and a maximum of 6 cc in total. (While PET may be used to identify GTV, MRI is still required for RT tx planning)
- A pathology review at the University of Miami of the outside biopsy material prior to enrollment.
- Psycho-Social Questionnaires:

- The Expanded Prostate Cancer Index Composite Questionnaire-SF12 (EPIC-SF12)
- Memorial Anxiety Scale for Prostate Cancer patients (MAX-PC)
- International Prostate Symptom Score (IPSS).

After enrollment and Prior to RT

- CT simulation.

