5.2 Evaluations during Radiation Therapy

- Weekly history and physical including performance status (Zubrod), and toxicity.

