14.5 Analysis plan

The main analysis of study findings will be done for all patients who meet evaluable criteria as stated in Section 14.3. As noted above, analyses of some secondary endpoints, including acute toxicity, psychosocial parameters, tissue and blood product-related biomarker distribution on US-guided biopsies, and initial MRI findings may be reported before the efficacy endpoints, including the primary endpoint. These secondary endpoints will be analyzed after all planned patients have been accrued, completed treatment and have a minimal potential follow-up of 3 months from the end of RT. An initial analysis of clinical outcome (efficacy) is planned after all patients have been assessed for PSA levels at 9 months and a final analysis will be done at the completion of the planned 5 year follow-up of all study patients. Statistical tests will be two-sided with 5% significance level.

Statistical analysis will include descriptive statistics for patient demographics and baseline disease characteristics. Counts and percentages will be used to summarize the distribution of categorical variables while median, range, mean and standard deviation will be used for continuous variables. Baseline characteristics will include age, race/ethnicity, PSA, PSA doubling time, pT-category, pathologic Gleason score, and performance status. Biomarker measurements and proteomic/genomic profiles obtained from baseline biopsy will also be summarized with descriptive statistics.[51]

Treatment received will be summarized by the number and duration of treatment delays, and the rates of discontinuation or completion. Safety analysis will include a detailed tabulation of acute and late occurring toxicity by type and grade. Additionally, we will estimate the cumulative incidence (from start of treatment) of grade 2+ and 3+ genitourinary (GU) toxicity and of grade 2+ and 3+ gastrointestinal

(GI) toxicity. Death without the toxicity of interest will be treated as a competing risk, and toxicity rates will be reported.

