Time to event endpoints will be analyzed by Kaplan-Meier (KM) or competing risk (CR) methods as indicated in Table 14.5.[53, 54] Where the Kaplan Meier method is used, point estimates and 2-sided 95% confidence intervals for event-free rates will be reported for selected times such as 1, 2 and 5 years from treatment start using Greenwood's variance and the log-log transform method. Median event-free or overall survival time, if attained, will also be reported. Cox regression models will be used to explore the prognostic effect of baseline characteristics as well as biomarkers and proteomic and genomic profiles. Regression findings will be expressed as hazard ratios and corresponding 95% confidence intervals. For analyses involving competing risks, cumulative incidence rates will be reported for selected times with corresponding 2-sided 95% confidence intervals based on the variance estimator of Aalen and the log-log transform method. Regression models investigating prognostic factors will be fit by the method of Fine and Gray. [55, 56] Where study data indicate that at most a small number of competing risk events have occurred, analysis will be simplified by treating such events as censored observations in a Kaplan-Meier analysis, since the resulting overestimation of the event rate will be negligible.

Table 14.5. Time-to-event endpoints.

Endpoint	Analysis	Events (earliest)	Competing risks	Censoring
Failure rate	CR	CF, BF, BF+ CF (within 6 months of each other). Start subsequent therapy. Death related to prca without prior evidence of failure.	Death unrelated to prca	Last clinical +PSA assessment
Toxicity rate (to be done separately for GI and GU)	CR	Onset of grade 2+ and 3+ toxicity	Start subsequent therapy Death, any cause	Last contact
Failure free survival (FFS)	KM	CF, BF, BF+ CF. Start subsequent therapy. Death, any cause.	n/a	Last clinical or PSA assessment
Prostate cancer mortality	CR	Death related to prca	Death unrelated to prca	Last contact
Overall survival (OS)	KM	Death, any cause	n/a	Last contact

KM: Kaplan-Meier. **CR:** competing risk. **BF:** Biochemical failure. **CF:** clinical failure. **prca:** prostate cancer. **GI:** gastrointestinal. **GU:** genitourinary.

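### No CTCAE GI/GU grade is scheduled before radiotherapy, so onset of grade 2+ and 3+ toxicity cannot be judged consistently in men who have all had a prostatectomy

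*Combined protocol and SAP*

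**What the plan says.** **Grading schedule.** Section 5.1 asks for a history and physical that includes "ability to perform daily activities (Zubrod performance status) within 8 weeks prior to protocol entry", laboratory tests, imaging, pathology review, EPIC-SF12, MAX-PC and IPSS. It asks for no toxicity or CTCAE symptom grade. Grading first appears in section 5.2: "Weekly history and physical including performance status (Zubrod), and toxicity". Sections 5.3 and 5.4 repeat it for the last week of radiotherapy and for follow-up. The calendar text for toxicity (Appendix I) agrees: "During RT and at all follow-up visits; use CTCAE 4.0".

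**Population.** Inclusion criterion C requires a "Minimum of 3 months since prostatectomy to allow for return of urinary continence and healing". It sets no maximum interval, and no criterion requires that continence has returned. In the site's preliminary series (section 1.4.6.1), "The median time to RT after prostatectomy was 18 months", with a range of 3 to 120.

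**Analysis.** Section 14.5 states that "we will estimate the cumulative incidence (from start of treatment) of grade 2+ and 3+ genitourinary (GU) toxicity", and the same for GI toxicity. Table 14.5 gives the event as "Onset of grade 2+ and 3+ toxicity". Neither place sets a baseline reference or a relatedness condition. GU and GI status is not among the baseline characteristics that 14.5 will summarise.

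**Stopping guidelines.** Section 14.6 counts grade 3 or higher GI/GU toxicity that is possibly, probably or definitely related to treatment.

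**The concern.** Criterion C shows that the protocol expects some urinary morbidity from surgery. A man can start radiotherapy with that morbidity unresolved, and his first CTCAE grade is then taken after treatment has begun. Whether a grade 2 urinary symptom at the first weekly visit is an onset depends on his state beforehand, and that state is not recorded on the same scale. One assessor may count a stable symptom and another may set it aside, and the plan gives no rule for choosing.

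Toxicity is a named secondary objective (section 2.2). The reported incidence could mix surgical morbidity with toxicity of the radiotherapy course in a proportion that cannot be recovered from the CTCAE data.

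**Working it through.** **1. Where a grade is scheduled.**

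| Time point | Section | CTCAE toxicity listed? |
|---|---|---|
| Before enrollment | 5.1 | No |
| After enrollment, before RT | 5.1 | No (CT simulation only) |
| Weekly during RT | 5.2 | Yes |
| Last week of RT | 5.3 | Yes |
| Follow-up | 5.4 | Yes |

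The cells of the calendar's toxicity row are blank in every column, including those where 5.2 to 5.4 require grading, so they are not used as evidence. The row's text and sections 5.1 to 5.4 carry the point.

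**2. Effect on cumulative incidence.** The plan states no figure for this, so the calculation is a scenario.

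- t = true rate of new grade 2+ GU toxicity. Illustrative value 12%, the 8-year IMRT figure in section 1.5.
- b = proportion with grade 2+ GU symptoms before RT. Not in the documents; assumed 5% to 30%.
- Assumptions: prevalent and new symptoms are independent, every prevalent symptom persists into RT, and every one is counted.

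Apparent incidence = 1 − (1 − t)(1 − b).

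| b | Apparent incidence | Events in 40 men (true: 40 × 0.12 = 4.8) |
|---|---|---|
| 5% | 1 − 0.88 × 0.95 = 16.4% | 6.6 |
| 10% | 1 − 0.88 × 0.90 = 20.8% | 8.3 |
| 20% | 1 − 0.88 × 0.80 = 29.6% | 11.8 |
| 30% | 1 − 0.88 × 0.70 = 38.4% | 15.4 |

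If only new or worsened events were counted, the estimate would stay at 12% in every row.

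**3. Stopping guidelines.** The plan's own figures come first. With x events in n men, the late posterior is Beta(0.2 + x, 1.8 + n − x). For 2 of 8, P(rate > 10%) = 82.6%, as stated in 14.6. The acute posterior is Beta(0.3 + x, 1.7 + n − x). For 3 of 8, P(rate > 15%) = 90.4%, the stated value. (The text of that example gives 4 patients assessed, but its 37.5% and 90.4% both correspond to 3 of 8.) The prior tails are 32% and 27%, also as stated.

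Next, let one pre-existing grade 3 symptom be misjudged as at least possibly related, so that the acute count rises from 1 to 2. The guideline is met at a posterior of 80%.

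| n | 1 event | 2 events | Guideline met at 2? |
|---|---|---|---|
| 5 | 51.5% | 85.2% | Yes |
| 10 | 25.6% | 59.0% | No |
| 20 | 5.8% | 21.2% | No |

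One such case changes the result at n = 5 but not at n = 10 or 20.

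As an upper bound, assume a true G3+ rate of 5% in each window and that every pre-existing G3+ symptom is misattributed. Apply the Table 14.6.1 boundaries after each man up to 40, with per-man rate 1 − 0.95(1 − b).

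| Assumed G3+ prevalence b | Per-man rate | Acute boundary met | Late boundary met |
|---|---|---|---|
| 0 | 5.0% | 4% | 9% |
| 5% | 9.75% | 18% | 37% |
| 10% | 14.5% | 41% | 69% |

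**The case against.** The strongest reply is that the plan's wording already excludes stable symptoms. Table 14.5 counts an onset. Section 11.2 treats a worsening of the patient's condition on study as an adverse event. Section 9.1 speaks of toxicity occurring within defined windows. This stands against a stronger reading that a reader might infer, namely that any man with stable post-surgical symptoms automatically becomes an event at his first weekly visit. The documents do not say that. They leave onset to be judged without a baseline grade and without a rule.

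It is also fair to say that pre-treatment information exists. The history and physical falls within 8 weeks before entry, IPSS and EPIC-SF12 are completed before enrollment, and section 15.4 requires source records of physical condition before involvement. It would be wrong to claim that there is no record. But the questionnaires are patient-reported, nothing maps them to CTCAE grades, and 14.5 links none of these sources to the toxicity endpoint.

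Three further limits stand:

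- **Stopping guidelines.** They already require treatment-relatedness, and section 11.2.2 provides the categories unrelated and unlikely. They are offered to the DSMC as guidelines, not as automatic stops. A reader might infer that they share the defect in full; they do so only through misattribution.
- **Boost toxicity.** A reader might take the miscounted events as boost toxicity. In a single-arm trial no baseline grade can separate the boost from the rest of the course.
- **Recent surgery.** Three months is only a minimum, and the preliminary series had a median of 18 months. The point needs only that some men start with symptoms.

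**Conclusion.** The point holds as a gap in measurement and event definition for a secondary endpoint. No CTCAE grade precedes radiotherapy, and the cumulative incidence analysis has neither a baseline nor a relatedness condition. Onset therefore cannot be judged consistently, and persisting surgical symptoms can be counted as toxicity of the radiotherapy course.

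The size is unknown. The range of 16% to 38% against a true 12% is an upper-bound illustration: the prevalences are assumed, every prevalent case is taken to persist and be counted, and the 12% comes from an 8-year IMRT report that the reference list describes as covering clinically localized disease, not salvage treatment. The stopping-guideline effect is secondary and depends on misattribution. The primary PSA endpoint is unaffected. This is a cheap improvement.

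**What to change.** - **Sections 5.1 and Appendix I:** add a CTCAE 4.0 GI/GU grade to the pre-enrollment history and physical.
- **Section 14.5 and Table 14.5:** define a toxicity event as grade 2+ (or 3+) that is new or at least one grade above that man's baseline grade. Under this rule a stable grade 2 symptom is not an event, while a rise from grade 1 to grade 2 is a grade 2+ event.
- **Section 14.6:** state that the baseline grade is used to support attribution. The boundaries need no change for this.
- **Men already enrolled:** assign the baseline grade from the recorded pre-treatment history and physical, and report it as retrospective.

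The cost is one CRF line at an existing visit and a few sentences in 14.5 and 14.6. Retrospective grades will be less precise than prospective ones.

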APPENDIX II. NATIONAL CANCER INSTITUTE (NCI) COMMON TOXICITY CRITERIA (CTC)

The NCI CTC can be viewed on-line at the following NCI web site:

<http://ctep.cancer.gov/reporting/ctc.html>

APPENDIX III. DATA AND SAFETY MONITORING PLAN

The Sylvester Comprehensive Cancer Center (SCCC) Data and Safety Monitoring Committee (DSMC) will monitor this clinical trial according to the Cancer Center's DSM Plan. In its oversight capacity, the DSMC bears responsibility for suspending or terminating this study.

DSMC oversight of the conduct of this trial includes ongoing review of accrual and adverse event data, and periodic review of response to treatment. The guidelines appearing in Sections 9.0 and 14.0 are offered for DSMC consideration in assessing adverse events and treatment response. In addition, the DSMC will review reports from all audits, site visits, or study reviews pertaining to this clinical trial and take appropriate action.

APPENDIX IV. ADDITIONAL ITEMS

For the safety of our patients, please refrain from using the following prohibited and/or misleading abbreviations in the treatment and dose modification sections of the protocol.

Abbreviation	Definition	Term to Use
U	For unit	Unit
IU	For international unit	International unit
Pharmacy abbreviations	Example, qd for daily	Daily
1.0 mg	Trailing zero	1 mg
.1 mg	Lack of leading zero	0.1 mg
Drug name abbreviations	Example, MS for morphine sulfate	Write out drug name
µg	microgram	mcg
d/c	Discharge	Discharge
Cc	cubic centimeter	ml (milliliter)
>	Greater than	Write out meaning
<	Less than	Write out meaning

APPENDIX V PERFORMANCE SCALES

ZUBROD SCALE

0	Fully active, able to carry on all pre-disease activities without restriction
1	Restricted in physically strenuous activity but ambulatory and able to carry work of a light or sedentary nature. For example, light housework, office work
2	Ambulatory and capable of all self-care but unable to carry out any work activities. Up and about more than 50% of waking hours
3	Capable of only limited self-care, confined to bed or chair 50% or more of waking hours
4	Completely disabled. Cannot carry on self-care. Totally confined to bed
5	Death

KARNOFSKY SCALE

100	Normal; no complaints; no evidence of disease
90	Able to carry on normal activity; minor signs or symptoms of disease
80	Normal activity with effort; some sign or symptoms of disease
70	Cares for self; unable to carry on normal activity or do active work
60	Requires occasional assistance, but is able to care for most personal needs
50	Requires considerable assistance and frequent medical care
40	Disabled; requires special care and assistance
30	Severely disabled; hospitalization is indicated, although death not imminent
20	Very sick; hospitalization necessary; active support treatment is necessary
10	Moribund; fatal processes progressing rapidly
0	Dead

Comparison between Zubrod and Karnofsky Scale

ECOG / WHO / Zubrod	Karnofsky
Zubrod 0	Karnofsky 90-100
Zubrod 1	Karnofsky 70-80
Zubrod 2	Karnofsky 50-60
Zubrod 3	Karnofsky 30-40
Zubrod 4	Karnofsky 10-20
Death	

These scales may be used interchangeably as documentation of performance status in the research record.
